## 8 Exposure

One of the objectives in the study is to collect AESIs and compare long-term clinical experience with specific important conditions between Firmagon and agonist therapies. The therapy regimens may change, e.g. from continuous treatment to intermittent, at the discretion of the investigator. This section defines exposure periods that are used in order to be able to make unbiased (continuous) treatment comparisons of treatment-emergent adverse events.

### 8.1 Exposure Periods

In order to limit bias from different treatment effects and overlapping treatment periods on reported adverse events, and to make data comparable to a greater degree, the total exposure period will be partitioned as follows.

At the Baseline Visit patients will be asked if they are on ADT and if so, when it was initiated. The date of Informed Consent is also recorded as part of the eCRF data collection. Start date of *main treatment period* will be considered to be the date at which both the informed consent has been signed, and the first dose has been administered. End date of main treatment period will be recorded as date of loss to follow-up, change in ADT, discontinuation of ADT, or end-of-trial visit, whatever comes first. If treatment continues after end of main treatment period (e.g. due to regimen change), a consecutive treatment period will be considered to be started. Consecutive treatment periods have a similar definition of end-of treatment period as the main treatment period.

In the case that the informed consent was not signed at time of first dosing, a “pre-consent period” is considered. This period ends when the informed consent is signed, at which time the “Main Treatment Period” starts, see Table 4.

**Table 4: Exposure periods for a patient dosed prior to signing the informed consent**

Event	First Dose of ADT	Signature of IC	Changing treatment regimen
Exposure Period	Pre-consent Period	Main Treatment Period	Post Main Treatment Period

It could also be that the patient signs the informed consent before being dosed. This scenario would lead to the definition of a “Pre-exposure Period”. However, an adverse event occurring before first dose is defined as non-treatment emergent and will not be reported.

Considering AESIs occurring during the “Main Treatment Period” can strengthen the validity of the comparison of the treatment effects on these AEs.

## **8.2 Extent of Exposure**

The extent of exposure (in months of treatment (and in mg)) from start of “Main Treatment Period” to end of last period will be summarised by treatment and presented by descriptive statistics.

Similarly, the extent of exposure (in months of treatment (and in mg)) from start of “Main Treatment Period” to end of “Main Treatment Period” will be summarised by treatment and presented by descriptive statistics. A similar table of the extent of exposure during the “Pre-treatment Period” will be supplied.

Number of subjects in the different periods will be summarized, with percentages relative to the number of subjects in the “Main Treatment Period”.

## **9 Efficacy**

The main objectives of this trial are to describe the risk of safety events of special interest. These analyses are described in Section 10. This section describes the analyses of changes in hepatic enzymes, fasting serum glucose, testosterone and PSA levels.

### **9.1 General considerations**

Efficacy parameters will be evaluated for the Safety Analysis Set, see Section 6.1. All statistical tests will be performed using a two-sided test at a 5% significance level.

#### **9.1.1 Visit Window**

No visits are mandated or prescheduled as a part of the study. Follow-up information will be collected at visits scheduled as a part of routine care, or will be collected via telephone interview if a visit does not occur during the data collection window.

The data collection windows will be centred on the actual visit dates. The width of the window is +/- 14 days. Should more than one lab data fall into the visit window the following rules will be applied, if possible:

- if a dosing is performed in visit window, the data collected closest in time, prior to the dosing, will be used
- if no dosing is performed in visit window, the median value of the lab data will be used.

#### **9.1.2 Missing Values and Drop-Outs**

Data will be presented based on the observed cases. No imputation of missing data (using LOCF or other techniques) is done.

#### **9.1.3 Baseline Data**

Baseline data is defined as the non-missing data, closest in time prior to first dose. If no such data is obtained the baseline value will be set to missing.

#### **9.1.4 Change in Fasting Serum Glucose and Serum Hepatic Enzymes from Baseline to Each Visit**

Change and percentage change from baseline in glucose and hepatic enzyme levels (alanine aminotransferase, aspartate aminotransferase, bilirubin and alkaline phosphatase) will be summarised by descriptive summary statistics for each treatment arm (median and inter-quartile range) as well as actual values by visit and treatment arm for the analyses set.

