## 2 Study Objectives and Endpoints

### 2.1 Objectives

#### Primary Objective

The primary objective of this observational study is to describe the risk of the following Adverse Event of Special Interest (AESI) in association with Firmagon treatment:

- Cardiovascular events
- Events related to decreased bone density, including new onset or progression of osteoporosis or osteopenia, and fractures
- New onset or exacerbation of glucose intolerance or type 2 diabetes mellitus
- Changes in hepatic enzyme levels

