### 2.2 Endpoints

#### Safety Endpoints

The following endpoints will be analysed in the study:

1. Rate of AESI
  - a. Incidence rate of cardiovascular events
  - b. Incidence rate of bone fracture, including osteoporotic/fragility fractures
  - c. Incidence rate of new onset or worsening osteoporosis or osteopenia

- d. Incidence rate of new-onset diabetes mellitus
  - e. Incidence rate of all-cause mortality
2. Occurrence of relevant laboratory value changes
- a. Changes in hepatic enzymes, fasting serum glucose, testosterone and PSA levels
  - b. Incidence rate of glucose intolerance

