### 10.4.1 Definition

The main objective of this observational study is to collect information on AESI. Specifically: cardiovascular events; new onset of diabetes mellitus; progression of osteoporosis or osteopenia; events associated with bone fractures (osteonecrosis); and all-cause mortality. The worsening of glucose intolerance based on lab data has been described in Section 9.1.5. Only events classified as serious will be considered.

Any AESI in the medical history occurring during the “Main Treatment Period” (or thereafter), or any adverse event of special interest in the adverse event report log occurring during the “Pre-consent Period” will be listed, as these possibly should be shifted from medical history to adverse event (or opposite).

In order to limit bias from different treatment effects and overlapping treatment periods and to make data comparable to a greater degree *only* AEs reported during the “Main Treatment Period” are considered (see Section 8.1 for details).

The AEs will be coded using MedDRA lowest level term (LLT). An AE included in any of the following Standardised MedDRA queries (SMQs), at the narrow search scope level, is defined as an event of special interest:

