## **10.7 Safety Laboratory Variables**

There is no planned collection of safety laboratory variables in the study.

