## Appendix 1 Markedly Abnormal Laboratory Safety Values, Vital Signs and ECGs

**Table 1: Markedly abnormal Criteria for Laboratory Tests**

Variable	Units	Markedly abnormal Criteria	
		Low	High
Haematology			
Haemoglobin	g/L	Male: $\leq 115$ Female: $\leq 95$	Not applicable
Haematocrit	Ratio	Male: $\leq 0.37$ Female: $\leq 0.32$	$\geq 0.56$
Total WBC	$10^9/L$	$\leq 2.8$	$\geq 16.0$
Eosinophils	%	Not applicable	$\geq 10$
Neutrophils	%	$\leq 15$	$\geq 90$
Lymphocytes	%	$\leq 10$	$\geq 80$
Monocytes	%	Not applicable	$\geq 20$
Basophils	%	Not applicable	$\geq 5$
Bands	%	Not applicable	$\geq 20$
Platelets	$10^9/L$	$\leq 75$	$\geq 700$
Total RBC	$10^{12}/L$	$\leq 3.5$	Not applicable
Clinical Chemistry			
AST (SGOT)	IU/L	Not applicable	$> 3xUNL$
ALT (SGPT)	IU/L	Not applicable	$> 3xUNL$
Alkaline phosphatase	IU/L	Not applicable	$> 3xUNL$ and 25% increase from baseline
GGT	IU/L	Not applicable	$> 3xUNL$
LDH	IU/L	Not applicable	$> 3xUNL$
Total bilirubin	$\mu\text{mol}/L$	Not applicable	$\geq 1.5xUNL$
Urea nitrogen	mmol/L	Not applicable	$\geq 10.7$
Creatinine	$\mu\text{mol}/L$	Not applicable	$\geq 177$
Total protein	g/L	$\leq 45$	$\geq 90$
Albumin	g/L	$\leq 25$	$\geq 65$
Sodium	mmol/L	$\leq 130$	$\geq 155$
Potassium	mmol/L	$\leq 3.0$	$\geq 5.8$
Chloride	mmol/L	$\leq 90$	$\geq 115$
Phosphorus	mmol/L	$\leq 0.5$	$\geq 1.9$
Calcium	mmol/L	$\leq 1.8$	$\geq 3.9$
Uric acid	mmol/L	Not applicable	Male: $\geq 0.62$

Variable	Units	Markedly abnormal Criteria	
		Low	High
			Female: $\geq 0.51$
Glucose	mmol/L	$\leq 2.8$	$\geq 10$
Total cholesterol	mmol/L	Not applicable	$\geq 8.0$
Urinalysis: Quantitative			
pH	None	$\leq 4$	Not applicable
Specific gravity	None	$\leq 1.005$	Not applicable
Urinalysis: Dipstick Chemistries			
Glucose	0 - 4+	Not applicable	Increase of 2 or more units from baseline
Casts		Not applicable	Increase of 2 or more units from baseline
Protein	0 - 4+	Not applicable	Increase of 2 or more units from baseline
Ketones	0 - 4+	Not applicable	Increase of 2 or more units from baseline
Blood (Hgb)	0 - 4+	Not applicable	Increase of 2 or more units from baseline
Urinalysis: Microscopic Variables			
RBC	no./hpf	Not applicable	$\geq 10$
WBC	no./hpf	Not applicable	$\geq 20$
Casts	no./hpf	Not applicable	Neg at baseline to positive on-treatment
Bacteria	no./hpf	Not applicable	Neg at baseline to positive on-treatment
Cells	no./hpf	Not applicable	Neg at baseline to positive on-treatment

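### Hepatic enzyme changes fall under the primary objective, but the only laboratory summary is median and inter-quartile range; the SAP body never counts patients above its own Appendix 1 limits

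*SAP*

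**What the plan says.** - **Objective.** The primary objective in SAP Section 2.1 is to describe risk. Its fourth item is "Changes in hepatic enzyme levels".
- **Endpoint.** In Section 2.2, hepatic enzymes are item 2a under the heading "Occurrence of relevant laboratory value changes". Item 2b, glucose intolerance, is worded as an incidence rate.
- **Analysis.** Section 9.1.4 covers ALT, AST, bilirubin and alkaline phosphatase. Change and percentage change "will be summarised by descriptive summary statistics for each treatment arm (median and inter-quartile range"), and actual values are shown by visit and arm as well. Median and inter-quartile range are the only statistics named.
- **AESI definition.** Section 10.4.1 lists the events that enter the rate analyses: "Specifically: cardiovascular events; new onset of diabetes mellitus; progression of osteoporosis or osteopenia; events associated with bone fractures (osteonecrosis); and all-cause mortality". There is no hepatic category there, in the regression models of Section 10.5.1 or in Appendix 4.
- **Thresholds.** Appendix 1 contains a table titled "Markedly abnormal Criteria for Laboratory Tests". Its limits are above 3 times the upper normal limit for ALT and AST, the same plus a 25% rise from baseline for alkaline phosphatase, and at least 1.5 times the upper normal limit for total bilirubin. No body section refers to this appendix.
- **Laboratory section.** Section 10.7 says: "There is no planned collection of safety laboratory variables in the study".

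**The concern.** Risk and occurrence are statements about how many patients are affected, out of how many. Section 9.1.4 describes the middle half of the distribution at each visit. Marked enzyme elevations lie in the upper tail and usually concern few patients, so the planned summary says little about them. Summarising by visit thins the picture further if elevations are transient and occur at different visits in different patients.

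Hepatic enzymes are the only one of the four primary items without an incidence analysis. Glucose is also a routine-care laboratory value, and Section 9.1.5 gives it a threshold-based incidence rate, so discretionary sampling does not explain the difference. At stake is whether this post-authorisation safety study reports any laboratory-based estimate of the risk of hepatic enzyme elevation.

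**Working it through.** **No figure to reproduce.** SAP Table 2 gives precision for cardiovascular events, fractures and diabetes only. The SAP states no expected rate, precision or power for hepatic enzymes.

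**Inputs.** The arm sizes, about 1000 Firmagon and 500 GnRH agonist patients, are from SAP Section 3. The share p of patients with a marked elevation is assumed, with 1% to 3% as the main range and 5% as a further case. Changes are taken as normal apart from the affected patients, in SD units.

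**Step 1: how far the planned statistics move.** If a share p moves to the extreme upper tail, the median of the whole group sits at quantile 0.5/(1−p) of the unaffected distribution, and the third quartile at 0.75/(1−p). With p = 0 these are 0 and 0.674.

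| p | New median, z(0.5/(1−p)) | New Q3, z(0.75/(1−p)) | Q3 shift |
|---|---|---|---|
| 1% | z(0.5051) = 0.013 | z(0.7576) = 0.699 | 0.024 |
| 2% | z(0.5102) = 0.026 | z(0.7653) = 0.723 | 0.049 |
| 3% | z(0.5155) = 0.039 | z(0.7732) = 0.749 | 0.075 |
| 5% | z(0.5263) = 0.066 | z(0.7895) = 0.805 | 0.130 |

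The size of the elevations does not enter the formulas: a value just above the limit and one far above it move the quartiles equally. The quartiles do respond, but too weakly at 1% to 3% to be recognised as a signal.

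**Step 2: what a count would show.** Exact (Clopper-Pearson) 95% intervals, assuming every patient has a measurement:

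| p | Firmagon, n = 1000 | GnRH agonist, n = 500 |
|---|---|---|
| 1% | 10: 1.0% (0.5 to 1.8%) | 5: 1.0% (0.3 to 2.3%) |
| 2% | 20: 2.0% (1.2 to 3.1%) | 10: 2.0% (1.0 to 3.6%) |
| 3% | 30: 3.0% (2.0 to 4.3%) | 15: 3.0% (1.7 to 4.9%) |

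Sampling is at the treating physician's discretion (Table 1, footnote c), so real denominators may be smaller and the intervals wider.

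**Step 3: which limits need a baseline.** The ALT, AST and bilirubin limits use the on-treatment value alone. The alkaline phosphatase limit needs a baseline, as does any shift table. Section 7 sets baseline to missing for Firmagon patients already on treatment at the baseline visit, and Section 9.1.3 does so where no pre-dose value exists. Those patients also have no change from baseline in Section 9.1.4, but they can still be counted against the three limits that need no baseline.

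**The case against.** **The plan follows the endpoint as written.** Item 2a says changes and only 2b says incidence rate; Sections 9.1.4 and 9.1.5 respect that split. This has some force. But the parent heading speaks of occurrence and the objective of risk, and neither is met by a median.

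**Other outputs may show a signal.** Hepatic events reported as adverse events enter the tables of Sections 10.3.1 and 10.3.2 by preferred term, intensity and seriousness, and serious ones get narratives. This stands. A reader might infer that a hepatic signal is bound to be invisible or that the primary question cannot be answered; the SAP does not support that. The route depends on investigator reporting, however, and does not analyse the laboratory endpoint.

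**Actual values and extremes.** Section 9.1.4 also presents actual values, but names no maximum, count or category. The minimum and maximum rule in Section 7 is for the study population tables, and a maximum shows one patient, not how many.

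**Appendix 1 looks like a template.** It has limits for women and full urinalysis criteria, so it does not prove that a hepatic threshold table was intended. The table specifications are a separate document (Section 14), so non-use can be established only for the SAP text. Both points stand. The limits nevertheless cover exactly the four analytes in Section 9.1.4.

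**Section 10.7.** A reader might see a contradiction with Section 9. There is none: no planned collection is consistent with analysing routine-care values, since Section 1 requires no study procedures.

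**Conclusion.** The point holds as a cheap improvement. For an item under the primary objective, the SAP specifies a laboratory summary that is nearly blind to a small affected minority, and its body never applies the hepatic limits it carries in Appendix 1. At an assumed 1% to 3% of patients with marked elevations, the median moves by at most about 0.04 SD and the third quartile by about 0.075 SD. A count would estimate the same share in 1000 patients with an interval from 0.5 to 1.8% (at 1%) or 2.0 to 4.3% (at 3%).

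The size rests on three assumptions: the rates are illustrative, the changes are roughly normal, and all patients are sampled. The insensitivity of quartiles to a small tail does not depend on the exact rate.

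**What to change.** Add to Section 9.1.4:

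1. By arm, the number and percentage of patients, with exact 95% CI, who have at least one on-treatment value meeting the Appendix 1 limit for ALT, AST, alkaline phosphatase or total bilirubin. The denominator is patients with at least one on-treatment measurement of that analyte. Give the rate per 100 patient-years alongside, and say which exposure period of Section 8.1 counts as on treatment.
2. A shift table from baseline to worst on-treatment value. Restrict this table and the alkaline phosphatase criterion to patients with a valid baseline, and report by arm how many are excluded.
3. The number of samples per patient-year by arm. Sampling is discretionary, and Section 3.1 notes that Firmagon is dosed monthly while agonists may be given less often. A difference in the share with at least one raised value could therefore reflect how often patients were tested.

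Cite Appendix 1 at that point. Optionally, add a cross-reference from Section 10.7 to Section 9 for clarity.

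The cost is a few sentences of SAP wording and two extra tables, with no new data collection. The remaining weakness is that the rates depend on sampling frequency, which item 3 discloses but does not remove.

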### **9.1.5 Incidence of Glucose Intolerance (Impaired Fasting Glycaemia)**

The protocol defines glucose intolerance as a fasting glucose level of 6.1-6.9 mmol/L (110mg/dl-125 mg/dL). (This corresponds to WHO's definition of impaired fasting glycemia [8].) The incidence rate of glucose intolerance will be analysed and presented as described in Section 10.5.1. Adjusting factors will be age, stage of disease and history of diabetes mellitus (as reported by the patient).

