#### 3.1 Schedule of Assessments

Patients will be enrolled after the initial decision (by the investigator) has been made to introduce Firmagon or GnRH agonist as per label indication for prostate cancer. Data will be collected at baseline and every 3 months ( $\pm$  4 weeks) for the first 2 years, then every 6 months ( $\pm$  6 weeks) for the remaining 3 years. Firmagon is dosed monthly, while GnRH agonists may be administered less frequently, therefore suggested data collection time points *may not always* coincide with treatment-related clinical visits. If necessary, telephone outreach may be used by sites to collect relevant data. Patients who discontinue ADT therapy will continue to be followed for safety outcomes in order to assess the long term safety associated with ADT.

A flowchart of *recommended* study assessments is provided in [Table 1](#).

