**Table 1 Study Flow Chart**

Visit	Baseline	Follow-up	
Time	0	0-2 years (3 months ( $\pm$ 4 weeks) between the visits)	2-5 years (6 months ( $\pm$ 6 weeks) between the visits)
Informed consent (a)	x		
Inclusion/exclusion criteria	x		
Demographics	x		
History/stage/histology of PCa	x	x	x
Body weight, height and waist circumference	x	x (b)	x (b)
Medical History	x		
Concomitant medications	x	x	x
Adverse events		x	x
ADT treatment		x	x
Fasting glucose, hepatic enzymes, DEXA bone scan	x (c)	x (c)	x (c)
PSA, testosterone	x (c)	x (c)	x (c)

- a) Written informed consent must be obtained prior to any study related data collection
- b) Height, weight, and waist circumference (waist circumference only if measured) should be collected at baseline and annually thereafter
- c) At the discretion of the treating physician, estimated to be every 3 – 6 months.

Since no visits are mandated or prescheduled as part of the study, but collected at visits scheduled as a part of routine care, the changes in hepatic enzymes, fasting serum glucose, testosterone and PSA levels, will be presented by visit intervals as dictated in Section 9.1.1. The reporting date of adverse events will not be changed.

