### **10.4.2 Incidence of Adverse Events of Special Interest**

A summary table will be prepared for the incidence of each AESI. For example, for cardiovascular events, the first AE in the class of the CV SMQs will be accounted for, while the other events will be disregarded. For the incidence rate, it will be the time to this event that is used. Should no event occur, patient is lost to follow-up, or completes the trial (without an event) it is the total observed exposure time that is used, while the patient does not contribute to the derived endpoint count.

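### The glucose-intolerance rate in SAP 9.1.5 has no testing-based at-risk time, so following the plan counts untested patient-years as event-free

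*SAP*

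**What the plan says.** SAP 2.2 lists the incidence rate of glucose intolerance as endpoint 2b, and glucose intolerance is named in the primary objective (2.1). Section 9.1.5 defines it purely by a laboratory band, "a fasting glucose level of 6.1-6.9 mmol/L (110mg/dl-125 mg/dL", and then states: "The incidence rate of glucose intolerance will be analysed and presented as described in Section 10.5.1". The covariates are fixed as follows: "Adjusting factors will be age, stage of disease and history of diabetes mellitus (as reported by the patient". None of them concerns testing.

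The model in 10.5.1 uses log person-years as its offset and does not say how person-years accrue. That rule is in 10.4.2: for a patient with no event, "it is the total observed exposure time that is used". The population is the Safety Analysis Set (9.1, 6.1), meaning dosed and consented patients, with no condition on having been tested.

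On testing, footnote c of Table 1 says: "At the discretion of the treating physician, estimated to be every 3 – 6 months". The Introduction states that the study requires no procedures. Section 9.1.1 adds that follow-up data "will be collected via telephone interview if a visit does not occur during the data collection window". On contact by arm, 3.1 says: "Firmagon is dosed monthly, while GnRH agonists may be administered less frequently".

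**The concern.** Full exposure time is a sensible denominator for adverse events, which can be reported at any contact. It does not suit a state that is invisible without a blood test. A patient who is never tested, or is last tested in year 1, can add up to five years of apparently event-free time and cannot add an event.

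Two results are at stake, with different certainty. The absolute Firmagon rate, which serves the primary objective, falls whenever some patients go untested, even if the arms are tested alike. The incidence rate ratio (IRR), which serves a secondary objective, is affected only if testing differs between arms. Nothing planned in 9.1.5 or 10.5.1 would show the reader how much of either figure reflects testing.

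**Working it through.** **1. The plan's own figure.** The SAP gives no rate or precision for glucose intolerance. The nearest is new-onset diabetes in Table 2: 2.90 per 100 patient-years, 95% CI 2.44 to 3.45. With 1,000 patients, five years and 10% uniform dropout (3.2):

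- Patient-years = 900 × 5 + 100 × 2.5 = 4,750
- Events = 2.90 × 47.5 = 137.75, taken as 138
- Exact Poisson CI for 138/4,750 = 2.44 to 3.43

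This reproduces the stated interval closely. All eight rows agree to about 0.03 per limit.

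**2. Inputs that are assumptions.** True rates of 2.9 (borrowed from diabetes), 5 and 10 per 100 patient-years, equal in both arms; the shares tested; test intervals of 3 or 6 months (the ends of the footnote c range); and how long the state lasts.

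**3. Effect on the absolute rate.** Let λ be the true yearly rate. Mean time to event or end of follow-up per tested patient is

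M = 0.9 × (1 − e^(−5λ))/λ + 0.1 × [1 − (1 − e^(−5λ))/(5λ)]/λ

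At λ = 0.05, M = 0.9 × 4.424 + 0.1 × 2.304 = 4.212 years, with λM = 0.2106 events. An untested patient adds 4.75 years and no event. With a share p tested:

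reported rate = pλM / [pM + (1 − p) × 4.75]

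At p = 0.5 this is 0.1053/4.481 = 2.35 per 100 patient-years. A simulation with 400,000 patients per arm, detecting the state only at tests, gives 2.33. For true rates of 2.9, 5 and 10 it gives 1.40, 2.33 and 4.34, with an IRR of 1.0 because both arms are affected alike.

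**4. Effect on the IRR if the share tested differs.** With 80% v 60% ever tested and λ = 0.05:

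- Firmagon: 0.1685/4.320 = 3.90
- Agonist: 0.1264/4.427 = 2.85
- Ratio: 1.37

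With 3- v 6-monthly tests the simulation gives 3.86 v 2.84, a ratio of 1.36. Expected events are about 168 and 63, so SE(log IRR) = √(1/168 + 1/63) = 0.148. Then ln 1.36/0.148 = 0.307/0.148 = 2.08, and the chance that the 95% CI excludes 1 is Φ(2.08 − 1.96), about 55%.

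| Scenario, true IRR = 1 | Reported IRR | CI excludes 1 |
|---|---|---|
| 50% tested in both arms | 1.0 | – |
| All tested, 3 v 6 months, state persists | 1.01 | – |
| 80% v 60% tested, 3 v 6 months | 1.36–1.41 | 37%–88% |
| 90% v 70% tested, 6 months in both | 1.30–1.35 | 33%–82% |
| All tested, 3 v 6 months, mean duration 1 year | 1.14–1.17 | – |
| All tested, 3 v 6 months, mean duration 3 months | 1.51–1.54 | – |

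Ranges cover true rates 2.9 to 10; a dash means not calculated.

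**5. After correction.** In the 80% v 60% case at a true rate of 5, limiting the denominator to tested patients gives 4.97 v 4.91, an IRR of 1.01. This run did not model patients whose testing stops part-way, which ending time at the last test is meant to handle. For short-lived states the correction is incomplete: with all patients tested at 3 v 6 months, the IRR stays at 1.08 to 1.52 for mean durations from 2 years down to 3 months.

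**The case against.** **The denominator is inferred.** Section 9.1.5 cites 10.5.1, not 10.4.2, and 2.2 lists glucose intolerance apart from the AESI rates. This is fair. But 10.4.3 names glucose intolerance among the AESIs, 10.4.2 holds the only no-event rule in the SAP, and 9.1.5 offers no other. The observed-cases rule in 9.1.2 concerns missing values, not person-time. A programmer following the document would use full exposure.

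**A difference between arms is not documented.** A reader might infer from 3.1 that Firmagon patients are tested more often, so that the IRR is biased against Firmagon. The SAP does not support that. It says only that agonists may be given less often, sets the same data-collection points for both arms, and gives one testing estimate for everyone. A dosing contact is not a fasting blood draw. Frequency alone also moves the IRR hardly at all if everyone is tested and the state persists. Nor would 10.5.1 declare harm: it says that a lower limit above 1 may suggest increased risk.

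**Some of this will be visible.** Attendance by visit interval (section 4) and glucose by visit and arm (9.1.4) will hint at uneven testing, but neither gives the share tested nor tests per patient-year, and neither corrects the rate.

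**Restricting to tested patients has its own bias.** Discretionary testing may follow risk. This stands and is carried into the fix.

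**Conclusion.** The point holds for the absolute rate and conditionally for the IRR. Following the SAP as written counts untested time as event-free, and the Firmagon rate is understated by roughly the untested share, about half if 50% are tested. That size assumes testing unrelated to risk; if physicians mainly test patients at higher risk, the shortfall is smaller.

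The IRR is distorted only if testing differs by arm. An assumed 80% v 60% ever tested gives 1.36 to 1.41 with no true difference, but no passage supplies those shares, and size and direction are unknown. The defect in the plan is the missing link between at-risk time and testing; a bias in favour of or against Firmagon is not shown.

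**What to change.** In SAP 9.1.5, give this endpoint its own at-risk rule:

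- Include patients with at least one post-baseline fasting glucose and no available baseline value already in or above the band.
- Count time from the start of the Main Treatment Period to the first qualifying fasting glucose or, if there is none, to the last fasting glucose in that period.
- Keep the full-exposure denominator as a sensitivity analysis.
- Beside the rate, report by arm the number and percentage tested and the fasting glucose tests per patient-year, and interpret the IRR in light of them.

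This needs SAP wording and a changed censoring date, using data already collected. The costs are fewer patients and patient-years, and possible selection, since discretionary testing may be driven by risk and could push the rate upward. A short-lived state is not fully corrected, which is why the testing figures must accompany the IRR.
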